4.2.3. Analysis Methods**4.2.3.1. Main Analytical Approach**

The number, proportion of participants with treatment success, and 95% Clopper-Pearson exact confidence interval (CI) will be provided for GPP and EP groups.

The primary endpoints will be analyzed using the primary estimand. After accounting for the ICE for the primary estimand, participants with missing data for the primary endpoints at Week 16 will be considered as nonresponders.

4.2.3.2. Supplementary Analyses

The same analysis in Main analytical approach in Section 4.2.3.1 will be applied to supplementary estimands.

4.3. Secondary Endpoints Analysis

Data will be summarized based on FAS and those will be presented by diagnosed disease (GPP or EP) unless specified.

4.3.1. Secondary Endpoints

4.3.2. Definition of Endpoint

4.3.2.1. Japanese Dermatological Association (JDA) Score

The JDA severity index for GPP consists of area of erythema with pustules, area of erythema (total), area of edema, fever, WBC, CRP, and serum albumin (provided in the study manual). The total score of JDA severity index for GPP ranges between 0 and 17 (0=best, 17=worst). Area of erythema with pustules, area of erythema (total), and area of edema are rated as 0 to 3. Fever, WBC, CRP, and serum albumin are rated as 0 to 2.

4.3.2.2. Body Surface Area (BSA)

The BSA is a commonly used measure of involvement of skin disease. It is defined as the percentage of surface area of the body involved with the condition being assessed. The handprint method for assessing BSA will be used in this study, where the surface area of the participant's hand including the palm and all 5 digits is used as a guide to estimate 1% BSA.

4.3.2.3. Investigator's Global Assessment (IGA)

The IGA documents the investigator's assessment of the participant's psoriasis at a given time point. Overall lesions are graded for induration, erythema, and scaling. The participant's psoriasis is assessed as cleared (0), minimal (1), mild (2), moderate (3), or severe (4) (provided in the study manual).

4.3.2.4. Psoriasis Area and Severity Index (PASI)

The PASI is a system used for assessing and grading the severity of psoriatic lesions and their response to therapy (provided in the study manual). In the PASI system, the body is divided into 4 regions: the head, trunk, upper extremities, and lower extremities. Each of these areas is assessed and scored separately for erythema, induration, and scaling, which are each rated on a scale of 0 to 4 and extent of involvement on a scale of 0 to 6. The PASI produces a numeric score that can range from 0 to 72. A higher score indicates more severe disease.

4.3.2.5. Dermatology Life Quality Index (DLQI)

The DLQI is a dermatology-specific health-related quality of life (HRQoL) instrument designed to assess the impact of the disease on a participant's HRQoL. It is a 10-item questionnaire that assesses HRQoL over the past week and in addition to evaluating overall HRQoL, can be used to assess 6 different aspects that may affect quality of life: symptoms and feelings, daily activities, leisure, work or school performance, personal relationships, and treatment. The total score ranges from 0 to 30 with a higher score indicating greater impact on QoL

For a partially answered questionnaire (eg, not all 10 answers in the DLQI questionnaire were available):

- If one question's answer is not available, this question will be scored 0. The total score will then be calculated.
- If two or more questions' answers are unavailable, the questionnaire is not scored. Hence, the total score and each of the 6 component scores will be set to missing.

4.3.2.6. EuroQuol 5-Dimension 5 Level Questionnaire

The EQ-5D-5L is a self-administered standardized measure of health status in a wide range of health conditions and treatments. The recall period for all items is "Today". The EQ-5D descriptive system is comprised of 5 items across the following 5 dimensions: mobility, self-care, usual activities, pain/discomfort and anxiety/depression. Each of the 5 dimensions uses a 5-point Likert response scale (Level 1 indicating no problem, Level 2 indicating slight problems, Level 3 indicating moderate problems, Level 4 indicating severe problems, and Level 5 indicating extreme problems). The EQ-5D also includes a visual analog scale that has endpoints labelled "best imaginable health state" and "worst imaginable health state" anchored at 100 and 0, respectively. Participants are asked to indicate how they rate their own health by indicating the point on the EQ VAS which best represents their own health on that day.

4.3.3. Estimand(s)

Not applicable.

4.3.4. Analysis Methods

For secondary endpoint, the observed data will be used without any imputation. Each endpoint will be summarized using descriptive statistics and its longitudinal change may be graphically displayed as appropriate.

4.3.4.1. CGI score

The number and proportion of participants with treatment success (for GPP: based on CGI scale according to JDA total score and for EP based on CGI scale) will be presented by postbaseline scheduled visit for GPP and EP respectively. The number and proportion of participants for each category will be also summarized with the same way.

4.3.4.2. JDA Score

JDA severity index total score will be analyzed only for the participants with GPP. The descriptive statistics of observed value and change from baseline will be presented by scheduled visit. The number and proportion of participants in each severity classification (mild(0-6), moderate(7-10), severe(11-17)) identified based on CRF will be also summarized by scheduled visit.

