### Type of Participant and Disease Characteristic(s)

2. The study participant has a diagnosis of GPP or EP at screening.
  - a. for GPP, a diagnosis must be classified based on the criteria for diagnosis of GPP by the Japanese Dermatological Association ([Appendix 8: Diagnostic Criteria of Generalized Pustular Psoriasis](#))
  - b. for EP, has a history of plaque-type psoriasis. In addition, has an involved BSA of lesion  $\geq 80\%$  at baseline.
3. Candidate for phototherapy or systemic treatment for psoriasis (either naïve or history of previous treatment).

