#### **Medical Conditions**

1. The study participant has a total score of JDA severity index for GPP  $\geq 14$  at baseline if participants have a diagnosis of GPP.

2. The study participant has a differential diagnosis of the erythroderma (eg, erythroderma caused by lymphoma or drug eruption) other than EP.
3. The study participant has a history of or current diagnosis or signs or symptoms of severe, progressive, or uncontrolled liver, renal; cardiac, vascular, pulmonary, gastrointestinal, endocrine, neurologic, hematologic, rheumatologic, psychiatric, or metabolic disturbances.
4. The study participant has a history of amyloidosis.
5. Known allergies, hypersensitivity, or intolerance to JNJ-77242113 or its excipients (refer to the IB).
6. The study participant had major surgery, (eg, requiring general anesthesia) within 8 weeks before screening, or will not have fully recovered from surgery, or has surgery planned during the time the participant is expected to participate in the study.

Note: Participants with planned surgical procedures to be conducted under local anesthesia may participate.

7. The study participant had transplanted organ (with exception of a corneal transplant >12 weeks before the first dose administration of study intervention).
8. All participants with:
  - suicidal ideation in the 26 weeks prior to screening that may be defined as a C-SSRS rating of: Wish to be Dead, Non-Specific Active Suicidal Thoughts, or Active Suicidal Ideation with Any Methods (Not Plan) without Intent to Act and is considered to be at risk by the investigator.

Participants  $\geq 18$  years if age with:

- suicidal ideation or suicidal behavior in the 26 weeks prior to screening that may be defined as a C-SSRS rating of: Suicidal Ideation with Intention to Act, Suicidal Ideation with Specific Plan and Intent, Actual suicide attempt, Interrupted suicide attempt, Aborted suicide attempt, or Preparatory behaviors for making a suicide attempt, and is considered to be at risk by the investigator based on an evaluation by a mental health professional.

Participants  $\geq 12$  to  $<18$  years of age with:

- suicidal ideation or non-suicidal self-injurious behavior in the 26 weeks prior to screening that may be defined as a C-SSRS rating of: Suicidal Ideation with Intention to Act, Suicidal Ideation with Specific Plan and Intent, or non-suicidal self-injurious behavior.

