**8.2.1.2. Japanese Dermatological Association Severity Index**

The JDA severity index for GPP consists of area of erythema with pustules, area of erythema (total), area of edema, fever, WBC, CRP, and serum albumin (provided in the study manual). The total score of JDA severity index for GPP ranges between 0 and 17 (0=best, 17=worst). Area of

erythema with pustules, area of erythema (total), and area of edema are rated as 0 to 3. Fever, WBC, CRP, and serum albumin are rated as 0 to 2 ([Iwatsuki 2010](#)).

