### 9.3.3. Secondary Efficacy Endpoints/Estimand Analysis

The secondary efficacy endpoints are:

- Proportion of participants with GPP or EP (for GPP: based on CGI scale according to JDA total score and for EP based on CGI scale) who experience treatment success over time.
- Change from baseline in the total score of the JDA severity index for GPP over time.
- Change from baseline in severity classification (mild, moderate, severe) of the JDA severity index for GPP over time.
- Change from baseline in BSA of involvement of lesion for EP over time.
- Proportion of participants who achieve an IGA score of cleared (0) or minimal (1) over time.
- Proportion of participants who achieve an IGA score of cleared (0) over time.
- Percent improvement from baseline in PASI over time.
- Change from baseline in DLQI score over time.
- Proportion of participants who achieve a DLQI score of 0 or 1 over time.
- Change from baseline in EQ-5D-5L (domain scores and VAS) over time.

All the secondary efficacy endpoints will be summarized descriptively. Graphical data displays may also be used to summarize the data.

The detailed methods of analysis and the data-handling rules for the key secondary endpoints will be specified in the SAP.

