4.3.4.6. DLQI

The following by scheduled visit analyses will be performed for DLQI score.

- The descriptive statistics of the observed value and change from baseline
- The number and proportion of participants who achieved DLQI score of 0 or 1 with $DLQI > 1$ at baseline

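### SAP 4.3.4.2 counts JDA severity classes visit by visit, which does not show the individual class change that is the secondary endpoint for GPP, least of all for participants who enter mild

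*SAP*

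**What the plan says.** Protocol 9.3.3 lists among the secondary efficacy endpoints "Change from baseline in severity classification (mild, moderate, severe) of the JDA severity index for GPP over time". The same endpoint is in Protocol sections 3 and 8.2.3.2 and in SAP 1.1.

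For this endpoint SAP 4.3.4.2 plans one summary, by scheduled visit: "The number and proportion of participants in each severity classification (mild(0-6), moderate(7-10), severe(11-17)) identified based on CRF". Protocol Appendix 9 gives the same three bands and cites the Japanese guideline for them. Neither document defines class improvement, and no baseline-to-visit cross-tabulation is planned.

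The item scores are stated consistently. For the skin items, "Area of erythema with pustules, area of erythema (total), and area of edema are rated as 0 to 3"; for the others, "Fever, WBC, CRP, and serum albumin are rated as 0 to 2". The total runs from 0 (best) to 17.

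Entry is limited from above only. Exclusion criterion 1 (Protocol 5.2) removes a candidate with GPP when "The study participant has a total score of JDA severity index for GPP" is 14 or more at baseline. Inclusion criterion 2a rests on diagnosis: "for GPP, a diagnosis must be classified based on the criteria for diagnosis of GPP by the Japanese Dermatological Association". No minimum score is set.

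SAP 4.3.4.2 also summarises the JDA total score and its change from baseline by visit, and SAP 4.4.2.2 does the same for the two components.

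**The concern.** The endpoint is a change within a participant, and the planned table is a set of marginal counts. A marginal table shows how many participants are mild at Week 0 and how many at Week 16. It does not show how many moved into mild, stayed there or left.

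The missing lower limit at entry makes this matter more. A GPP participant with a baseline total of 0 to 6 is already in the best class. Nothing that happens afterwards can move that participant to a better one, and at every later visit without worsening the participant adds one to the mild row, beside those who came down from moderate or severe. A reader who takes a large mild row as evidence of response would be counting some participants for where they began. With about 8 GPP participants, each one is 1/8 = 12.5 percentage points.

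Mild entry is plausible under the protocol. Inclusion criterion 4 allows stable methotrexate, cyclosporine or retinoid at entry, and Appendix 8 keeps in the GPP category cases whose recurrence is held down by ongoing treatment.

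**Working it through.** **Inputs.** Item ranges: Protocol 8.2.1.2 and SAP 4.3.2.1. Bands: SAP 4.3.4.2 and Protocol Appendix 9. Entry limit: Protocol 5.2, criterion 1. Target of 8 GPP participants: SAP section 5.

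**1. The stated range reproduces.** Three items of 0 to 3 and four of 0 to 2 give a maximum of 3×3 + 4×2 = 9 + 8 = 17 and a minimum of 0, as stated. The bands hold 7 + 4 + 7 = 18 totals and cover 0 to 17 without gap or overlap.

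**2. Baseline totals allowed.** Totals 0 to 13 are 14 values: 7 mild (0–6), 4 moderate (7–10) and 3 severe (11–13). These are score values, not participants, and say nothing about how often each will occur.

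**3. Which falls change the class.** From baseline total b there are b possible lower totals, so there are 0 + 1 + … + 13 = 91 possible falls.

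| Baseline class | Possible falls | Falls with no class change |
|---|---|---|
| Mild (0–6) | 21 | 21 |
| Moderate (7–10) | 34 | 6 |
| Severe (11–13) | 36 | 3 |
| All | 91 | 30 |

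Every fall from a mild baseline leaves the class unchanged. A fall from 6 to 0 is mild to mild and leaves the mild count as it was. Falls from 7 to 6 and from 7 to 0 are both moderate to mild, and each raises the count by one.

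**4. What the counts determine.** Mild at a visit = mild at baseline − those who left mild + those who entered mild. The table gives the first two of these four quantities, hence only the difference between the last two. As an illustration, assume 8 GPP participants, 4 mild and 4 moderate at baseline, with 6 mild and 2 moderate at Week 16:

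- Case A: 2 go from moderate to mild and nobody worsens. Mild = 4 − 0 + 2 = 6.
- Case B: 4 go from moderate to mild and 2 from mild to moderate. Mild = 4 − 2 + 4 = 6.

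The planned table is identical in both, although case A has 2 improved and 0 worsened, and case B has 4 improved and 2 worsened.

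**5. Dependence on the number entering mild.** Let k of 8 enter mild. The documents do not give k, so the range is 0 to 8 and the mild row starts at k/8, from 0% to 100%. At k = 0, everyone found mild later has improved in class, and the mild row reads correctly. At k = 8, no class improvement is possible.

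**The case against.** The strongest reply is that the information is not lost. The sentence before the class summary in SAP 4.3.4.2 plans the total score and its change from baseline, so a fall from 6 to 0 appears as −6 and one from 7 to 6 as −1. All five CGI categories, IGA 0 and IGA 0/1, PASI percent improvement and the JDA components are also summarised. This stands, and it confines the point to one endpoint.

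Second, the baseline mix is probably visible. The class summary is by scheduled visit, whereas the CGI summary is restricted to post-baseline visits, and SAP Appendix 2 summarises baseline JDA severity. This stands in part: a reader may see how many began mild, but step 4 shows that this still does not recover individual movement.

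Third, the bands belong to the published scale and are used identically in both documents. This stands. Any banded scale has a floor and cut-points, and that is not a planning error.

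A reader might go further and infer that the plan scores a fall from 7 to 6 as improvement and complete clearance from 6 as failure, or that it caps an improvement rate. The documents do not support this: the SAP never labels a class change as improved and plans no improvement rate. A reader might also infer that the lowest class must be split at 0. That would only move the artefact: 6 to 1 would still show no change, and 1 to 0 would become a class change.

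**Conclusion.** The point holds in a limited form and is minor. The planned summary does not measure the change named in the endpoint, because visit-by-visit class counts do not identify who changed class. Participants who enter mild cannot move to a better class and, in the counts, cannot be told apart from those who improved into mild.

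The size depends on how many enter mild, which is unknown (0 to 8 of about 8). The conclusion rests on the absence of a minimum baseline score and on SAP 4.3.4.2 being the whole planned analysis of this endpoint.

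It would be wrong to conclude that the trial hides clearance or that its efficacy result is biased. The total-score and other summaries capture improvement, the primary endpoint does not use the severity classes as its outcome, and SAP section 2 plans no formal testing, so no error rate is affected.

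**What to change.** In SAP 4.3.4.2, add for GPP participants a shift table by visit of baseline class against post-baseline class, with the number in each baseline class shown. Limit any statement about class improvement to participants whose baseline class can improve, that is moderate or severe. Because SAP 4.3.4 uses observed data without imputation, a column for missing class would keep the row totals fixed.

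Keep the three published classes. Optionally, add the count with a total score of 0 as a descriptive row; this needs no new class.

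The SAP already follows this practice elsewhere. It plans shift summaries for laboratory grades (4.5.3.1), C-SSRS categories (4.5.3.3) and PHQ-9 (4.5.3.5). For the DLQI it plans "The number and proportion of participants who achieved DLQI score of 0 or 1 with" a baseline score above 1. That is a threshold endpoint, so the parallel is partial, but it too leaves out participants who had already met the target.

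The data are already collected: the JDA index is scheduled at every efficacy visit. The cost is SAP wording and one small table, with sparse cells at about 8 participants.

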4.3.4.3. BSA Involvement by Psoriatic Lesions

For EP patients, BSA Involvement (%) and its change from baseline will be summarized using descriptive statistics for each scheduled visit.

4.3.4.4. IGA score

The number and proportion of the participants who achieve an IGA score of cleared (0) or minimal (1) will be presented by scheduled visit. In addition, the number and proportion of the participants who achieve an IGA score of cleared (0) will also be presented.

The proportion of participants with IGA total average score (cleared (0), minimal (1), Mild (2), Moderate (3), Severe (4)) by scheduled visit will be also summarized.

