### **8.2.1.5. Investigator's Global Assessment**

The IGA documents the investigator's assessment of the participant's psoriasis at a given time point. Overall lesions are graded for induration, erythema, and scaling. The participant's psoriasis is assessed as cleared (0), minimal (1), mild (2), moderate (3), or severe (4) (provided in the study manual).

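### The IGA 0/1 and IGA 0 rates have no baseline condition, unlike the DLQI 0/1 rate, so a GPP participant who enters at target can be counted as achieving it

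*SAP*

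**What the plan says.** SAP 4.3.4.4 defines the first IGA rate by stating that the number and proportion of participants "who achieve an IGA score of cleared (0) or minimal (1) will be presented by scheduled visit". For clearance it adds that "the number and proportion of the participants who achieve an IGA score of cleared (0) will also be presented". Neither sentence refers to the baseline score. The population comes from the opening of SAP 4.3: "Data will be summarized based on FAS and those will be presented by diagnosed disease (GPP or EP) unless specified". The FAS in SAP section 3 is everyone who received at least one dose.

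SAP 4.3.4.6 handles the corresponding DLQI rate differently. It counts "participants who achieved DLQI score of 0 or 1 with $DLQI > 1$ at baseline". SAP 4.4.2.1 carries the DLQI approach over to CDLQI.

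The protocol (8.2.3.2 and 9.3.3) lists the IGA and DLQI proportions without a baseline condition on either. The SAP therefore added a condition for DLQI and none for IGA. SAP 4.8, which lists departures from the protocol, covers only laboratory tests and physical examination, so the DLQI condition is not declared there.

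**The concern.** The plan uses the same word, achieve, for two proportions but builds them on different rules. For DLQI, a participant already at 0 or 1 before treatment is set aside. For IGA, such a participant stays in the denominator and counts as a success at every visit where the score has not risen.

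This matters mainly for GPP. EP participants must have at least 80% of body surface involved at baseline (Protocol 5.1, criterion 2b), which makes an entry IGA of 0 or 1 implausible. The GPP criteria have no such floor. The study has a single arm, so no control group shows how many participants would sit at IGA 0/1 without the study drug. With a target of 8 GPP participants, one person moves the numerator by 1/8 = 12.5 points.

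**Working it through.** The documents give no expected IGA rate, and the sample size rests on feasibility (SAP section 5), so there is no planned figure to reproduce. The check has two parts.

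**1. Can a GPP participant enter at IGA 0 or 1?**

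- Protocol 5.1, criterion 2a, requires the JDA diagnosis and no minimum severity score.
- The only severity limit is a ceiling. Exclusion criterion 1 in Protocol 5.2 begins "The study participant has a total score of JDA severity index for GPP" and removes scores of 14 or more.
- Protocol 5.1, criteria 4a and 4b, allows stable methotrexate, cyclosporine or retinoid.
- Protocol Appendix 8 does not rule out GPP whose recurrence is held down by ongoing treatment.
- The IGA does not cover everything that drives GPP severity. Protocol 8.2.1.5 says: "Overall lesions are graded for induration, erythema, and scaling". Pustules, oedema, fever and the laboratory items of the JDA index (Appendix 9) are not among its items.

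No criterion prevents a baseline IGA of 0 or 1 in GPP. Equally, no text shows that it will occur.

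**2. How far would it move the rate?**

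Assume 8 GPP participants, all observed at the visit. Let k be the number who enter at IGA 0/1 and are still there, and r the number of others who reach IGA 0/1.

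- Rate under SAP 4.3.4.4: (k + r)/8.
- Rate under the DLQI-style rule: r/(8 − k).

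| k | r | SAP 4.3.4.4 | Baseline-restricted | Difference (points) |
|---|---|---|---|---|
| 0 | any | r/8 | r/8 | 0 |
| 1 | 0 | 1/8 = 12.5% | 0/7 = 0% | 12.5 |
| 1 | 2 | 3/8 = 37.5% | 2/7 = 28.6% | 8.9 |
| 1 | 3 | 4/8 = 50.0% | 3/7 = 42.9% | 7.1 |
| 1 | 4 | 5/8 = 62.5% | 4/7 = 57.1% | 5.4 |
| 2 | 0 | 2/8 = 25.0% | 0/6 = 0% | 25.0 |
| 2 | 2 | 4/8 = 50.0% | 2/6 = 33.3% | 16.7 |
| 2 | 4 | 6/8 = 75.0% | 4/6 = 66.7% | 8.3 |

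The documents do not say what share of GPP participants would enter at target. If it were 5%, 10% or 20% (assumed values), the chance of at least one among 8 is 1 − 0.95^8 = 34%, 1 − 0.90^8 = 57% or 1 − 0.80^8 = 83%.

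The restriction can also work the other way. Suppose the one participant who entered at target worsens and three others reach it. The unrestricted rate is 3/8 = 37.5% and the restricted rate is 3/7 = 42.9%, because the restriction has removed a failure.

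**The case against.** The strongest reply is that the IGA analysis follows the protocol and the DLQI rule is the departure. IGA 0/1 can be reported as a disease state, and remaining there is informative in a recurrent disease, particularly as Protocol 6.9.1.1 has background methotrexate and cyclosporine tapered after Week 16. The worsening example above shows that restriction is not automatically the more conservative choice. This stands, and it is why the unrestricted rate should not be replaced.

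A second reply is that the planned outputs already reveal the problem. Baseline IGA is summarised and disease characteristics are listed (SAP Appendix 2), and the five IGA categories are tabulated by visit. SAP 4.3.4.4 tabulates by scheduled visit, whereas 4.3.4.1 limits CGI to postbaseline visits, so a Week 0 IGA row may appear. With 8 per group a careful reader could work it out. This also stands, but the rate itself would carry no such warning.

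A third reply is that entry at target is less likely than the missing floor suggests. Every participant must be a candidate for phototherapy or systemic treatment (Protocol 5.1, criterion 3), the diagnostic features include widespread redness, and washouts apply to most other therapies. These points lower the probability but do not exclude the case.

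A reader might infer that GPP participants with little scaling or induration will in fact be credited as responders. The documents do not support that. Erythema is graded too, and SAP 4.3.4.4 describes the score as an average without giving the rule, which sits in the study manual. If the score were the rounded mean of three items each graded 0 to 4 (assumed), no induration, no scaling and erythema 4 would give 4/3 = 1.33, hence IGA 1. Under another rule the same participant might score higher.

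A reader might also ask for a rule restricting percent PASI improvement (SAP 4.3.4.5) to baselines above 0. Percent improvement from zero is undefined in any case, so that rule would change no result.

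**Conclusion.** The point holds as a small inconsistency with an inexpensive remedy. The SAP conditions DLQI 0/1 on baseline but not IGA 0/1 or IGA 0, and the GPP entry criteria leave room for a participant to start at the IGA target. The size is conditional. It is zero if nobody enters at target. In the scenarios above it is 5.4 to 12.5 points for one participant who stays there and 8.3 to 25.0 points for two, assuming 8 participants observed and 0 to 4 new responders.

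The affected rates are secondary and descriptive. SAP section 2 plans no formal test, and Clopper-Pearson intervals are specified only for the primary endpoint (SAP 4.2.3.1), so no confidence interval for the IGA rates is at stake. The primary CGI endpoint compares with Week 0 and is unaffected, and EP is in practice unaffected. It would go too far to read this as showing that the IGA results in GPP are inflated.

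**What to change.** In SAP 4.3.4.4, keep both unrestricted rates as the protocol defines them and add beneath them:

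- IGA 0/1 among participants with baseline IGA of 2 or more;
- IGA 0 among participants with baseline IGA of 1 or more;
- the number already at each target at baseline, using the baseline defined in SAP 4.1.2.

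In SAP 4.8, declare these added rows and the existing restriction of DLQI 0/1 to baseline DLQI above 1.

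The cost is about one sentence in 4.3.4.4, an extra row for each rate, and an entry in 4.8. No new data are needed, since IGA is already assessed at Screening and Week 0. The drawback is a possibly smaller GPP denominator in the added rows. If nobody enters at target, those rows repeat the unrestricted ones.
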